6.9.2.2. Secondary Pharmacodynamic Analyses

The following measurements are secondary endpoints in the study to compare the effect of tirzepatide 15 mg versus placebo after 18 weeks (± 1 week) of treatment.

Appetite and Food Intake

Secondary PD measures to assess the effect of tirzepatide 15 mg versus placebo on appetite and food intake:

- change from baseline to Week 18 in appetite VAS assessed during sMMTT for
 - o 4 individual ratings: hunger, fullness, satiety, prospective food consumption
 - o 4 individual ratings: desire for 4 specific foods (sweet, salty, savory, and fatty)
 - overall appetite score

 all at 5 time points during sMMTT respectively: -10 (fasting), 60, 120, 180, 240 minutes

Note: The aim of the appetite VAS is to determine the effects of study treatments on appetite sensations and desire for specific foods.

The VAS scales will be analyzed as continuous variables on the 0 to 100 scale for individual components:

- For the above first 4 individual ratings, 0 = Not at all, 100 = Extremely
- For the last 4 individual ratings on desire for specific foods, 0 = Yes, very much, 100 = No, not at all

All 8 individual VAS scores (for each component) will be documented in electronic Case Report Form (eCRF). Overall appetite score is calculated as the average of the 4 individual scores (Flint et al. 2000; Flint et al. 2013; van Can et al. 2014) as follows:

```
overall appetite score = (satiety + fullness + [100 - prospective food consumption] + [100 - hunger]) / 4
```

The higher overall appetite score indicates less appetite, and the lower score indicates more appetite.

The above appetite VAS scores parameters (overall and 8 individual scores) will be analyzed using ANCOVA to compare the effect of tirzepatide versus placebo at each of 5 timepoints during sMMTT, respectively.

- ➤ Independent variables: treatment as a factor, baseline as a covariate
- Response variable: change from baseline to Week 18.

Time profile plots of appetite VAS parameters (mean \pm standard deviation) during sMMTT (over 5 time points) will be provided by treatment for baseline and Week 18.

- change from baseline to Week 18 in food intake assessed by ad libitum meal test at
 - o lunch
 - o dinner
 - lunch and dinner combined

Each for the following 11 food intake variables:

- total food intake
 - o g (the amount of grams of food consumed)
 - o kcal (energy intake)
- carbohydrate
 - o g
 - o kcal
 - o percent of energy (carbohydrate [kcal]/energy intake [kcal])
- protein
 - og

- o kcal
- o percent of energy (protein [kcal]/energy intake [kcal])
- fat (saturated and unsaturated)
 - o g
 - kcal
 - o percent of energy (fat [kcal]/energy intake [kcal])

Note: Food intake will be quantified separately for lunch, dinner, and combined for lunch and dinner. The amount of grams of fat, carbohydrates and protein consumed during lunch and during dinner will be documented in eCRF. There are 4 kcal in a gram of carbohydrate or protein, and 9 kcal in a gram of fat will be used to calculate energy intake related variables.

The above food intake parameters (at lunch, at dinner, and at lunch and dinner combined) will be analyzed using ANCOVA to compare the effect of tirzepatide versus placebo:

- ➤ Independent variables: treatment as a factor, baseline as a covariate
- Response variable: change from baseline to Week 18

Energy Expenditure (EE)

Secondary PD measures to assess the effect of tirzepatide 15 mg versus placebo on parameters of EE:

• change from baseline to Week 18 in 24-hour EE

The baseline 24-hr EE will be analyzed with ANOVA with independent variable, treatment as a factor.

At Week 18, the 24-hour EE will be analyzed with 2 ANCOVA models (similar to primary endpoint SMR)

- ➤ Model 1:
 - Independent variables: treatment as a factor, baseline 24-hr EE (kcal/day), change from baseline to Week 18 in fat free mass, and change from baseline in fat mass as covariates.
 - Response variable: change from baseline to Week 18 in 24-hr EE.
 - Where Fat Mass = DXA Region Fat (%)/100 * DXA Weight
 - Where Fat Free Mass = DXA Weight Fat Mass.
- ➤ Model 2 (additional analyses):
 - o Independent variables: treatment as a factor, baseline 24-hr EE (kcal/day), change from baseline to Week 18 in DXA weight as covariates
 - o Response variable: change from baseline to Week in 24-hr EE

Additional analyses may be conducted as follow:

- Step 1: conduct ANCOVA model with
 - o Independent variables: baseline fat free mass, baseline fat mass, age, sex
 - o Response variable: baseline 24-hr EE
 - Where Fat Mass = DXA Region Fat (%)/100 * DXA Weight

- Where Fat Free Mass = DXA Weight Fat Mass.
- Step 2: with estimated model from Step 1 to predict 24-hr EE at Week 18 using
 - Week 18 fat free mass, Week 18 fat mass, age, sex
- Step 3: calculate:
 - magnitude of residual 24hr EE at Week 18
 - = 24hr EE measured at Week 18 24hr EE predicted at Week 18 from Step 2
- Step 4: conduct ANOVA on residual 24-hr EE at Week 18 from Step 3 to compare tirzepatide to placebo

Substrate Oxidation Rate

Secondary PD measures to assess the effect of tirzepatide 15 mg versus placebo on parameters of substrate oxidation rates:

Respiratory quotient

- change from baseline to Week 18 in 24-hour respiratory quotient (RQ; ratio)
- change from baseline to Week 18 in sleep RQ (ratio)
- change from baseline to Week 18 in duration of periods with RQ<0.80 (minute)

The above RQ parameters will be analyzed with ANCOVA model

- ➤ Independent variables: treatment as a factor, baseline RQ parameter value as a covariate
- ➤ Response variable: change from baseline to Week 18 in RQ parameter

Protein, fat, carbohydrate oxidation

- change from baseline to Week 18 in protein oxidation (g/day)
- change from baseline to Week 18 in fat oxidation (g/day)
- change from baseline to Week 18 in carbohydrate oxidation (g/day)

The above oxidation rates parameters will be analyzed with

- Step 1: calculate adjusted oxidation parameters Adjusted oxidation rate (g/day) = oxidation rate (g/day) / 24-hr EE (kcal/day) * 1000 (kcal/day)
- ➤ Step 2: ANCOVA model
 - Independent variables: treatment as a factor, baseline adjusted oxidation rate as a covariate
 - Response variable: change from baseline to Week 18 in adjusted oxidation rate parameters

Note: 24-hr energy expenditure, RQ, protein oxidation, fat oxidation, and carbohydrate oxidation are calculated based on 23-hour measurement period and extrapolated to 24 hours. RQ will also be calculated for sleep period and extrapolated to 24 hours. The calculated 24-hr EE, 24 hr RQ, sleep RQ (in Event Data), duration of period with RQ<0.8, and 24-hr substrate oxidation (protein, fat, carbohydrate oxidation) will be provided in datasets to statisticians/programmers.

The average value of nonmissing measurements at Days -3, Day -2 (two 23-hr sessions) will be used as value for baseline, and the average value of nonmissing measurements during Days 123, Day 124 will be used as value for Week 18.

Body Weight and Body Composition

Secondary PD measures to assess the effect of tirzepatide 15 mg versus placebo on parameters of body weight, and body composition using DXA scan:

- change from baseline to Week 18 in
 - o body weight (scale weight; kg)

Note: Body weight is measured twice at each visit, and the average of non-missing measurements will be used for analyses.

Body weight was measured at baseline Day -1 (lead in) and multiple times post baseline. Plots of mean body weight and mean change from baseline values over time will be provided by treatment. The change from baseline to Day 8, Day 15, Day 22, Day 29, Day 36, Day 43, Day 50, Day 57, Day 64, Day 71, Day 78, Day 85, Day 92, Day 99, Day 106, Day 113, and Day 120-Day 125 (average of nonmissing measurements at Days 120, 123, 124, 125 used) will be analyzed using a mixed-model repeated measures (MMRM) method with restricted maximum likelihood (REML) estimation.

- > Independent variables: treatment, time, and treatment-by-time interaction as fixed effects, baseline body weight as a covariate, and patient as a random effect
- Response variable: change from baseline in body weight

An unstructured covariance structure will be used to model the relationship of within-subject errors. If this model fails to converge, the following variance covariance structures will be tested in order until convergence is achieved:

- heterogeneous Toeplitz
- heterogeneous first order autoregressive
- heterogeneous compound symmetry
- Toeplitz
- first order autoregressive, and
- compound symmetry.

The first covariance structure that converges will be used.

- change from baseline to Week 18 in
 - o body fat-free mass (kg)
 - o body fat mass (kg)
 - o percentage of body fat mass (total region % of fat)

Note: DXA scan parameters: DXA Weight and DXA Region Fat (%) will be provided in datasets to statisticians. Fat mass and fat free mass will be calculated for 2 DXA scans on the same day:

• Fat Mass = DXA Region Fat (%)/100 * DXA Weight

• Fat Free Mass = DXA Weight – Fat Mass

The mean value of nonmissing measurements from the 2 DXA scans on the same day will be calculated for analyses.

The above body composition parameters will be analyzed using ANCOVA to compare the effect of tirzepatide versus placebo:

- Independent variables: treatment as a factor, baseline body composition parameter as a covariate
- Response variable: change from baseline to Week 18 in body composition parameter.

Lipid Metabolism

Secondary PD measures to assess the effect of tirzepatide 15 mg versus placebo on parameters of lipid metabolism:

- change from baseline to Week 18 in lipid metabolism measurements during sMMTT in:
 - triglycerides
 - o cholesterol
 - o LDL cholesterol
 - VLDL cholesterol
 - HDL cholesterol
 - o FFA
 - o glycerol
 - o 3-hydroxybutyrate (ie beta-hydroxybutyrate)
 - o acylcarnitines

All the above lipid metabolism lab measurements will be calculated for (1) fasting; (2) total AUC_{0-4hr} ; (3) incremental AUC_{0-4hr} for analyses.

Note: For fasting measurements, it is collected on Day -4 (lead in, 10 minutes prior to sMMTT), Day 29 (Week 5), Day 57 (Week 9), Day 122 (Week 18; 10 minutes prior to sMMTT). For AUC parameters, it is derived for baseline and Week 18 during sMMTT.

Note: See Section 6.9.1 for AUC calculation details. All these fasting lab measurements and AUCs will be reported in both International System of Units (SI Units) and conventional units.

- change from baseline to Week 18 in lab measurements during sMMTT of:
 - o ApoB-48
 - o ApoB-100
 - o ApoC-III
 - o LPL

All the above lipid metabolism lab measurements will be calculated for (1) fasting; (2) total AUC_{0-4hr}; (3) incremental AUC_{0-4hr} for analyses.

Note: For fasting measurements, it is collected Day -4 (lead in, 10 minutes prior to sMMTT), Day 29 (Week 5), Day 57 (Week 9), Day 122 (Week 18; 10 minutes prior to sMMTT). For AUC parameters, it is derived for baseline and Week 18 during sMMTT.

Note: See Section 6.9.1 for AUC calculation details. All these fasting lab measurements and AUCs will be reported in both SI Units and conventional units.

The above available laboratory fasting parameters will be analyzed in a manner similar to the secondary PD analysis on body weight using MMRM to compare the effect of tirzepatide versus placebo.

- ➤ Independent variables: treatment, time, and treatment-by-time interaction as fixed effects, baseline as a covariate, and patient as a random effect
- Response variable: change from baseline

The above available laboratory AUC parameters during sMMTT will be analyzed using ANCOVA to compare the effect of tirzepatide versus placebo:

- ➤ Independent variables: treatment as a factor, baseline as a covariate
- Response variable: change from baseline to Week 18.

Time profile plots of the lab measurements (mean \pm standard deviation) during sMMTT (over 6 time points) will be provided by treatment for baseline and Week 18.

- change from baseline through Week 18 in fasting concentration of:
 - o leptin
 - o adiponectin
 - o IGFBP 1
 - o IGFBP 2

The above fasting leptin, adiponectin, IGFBP 1 and 2 will be analyzed in a manner similar to the secondary PD analysis on body weight using MMRM since the lab tests are scheduled to be measured at baseline (Day -4) and 3 times postbaseline (Day 29 [Week 5], Day 57 [Week 9] and Day 122 [Week18]).

- ➤ Independent variables: treatment, time, and treatment-by-time interaction as fixed effects, baseline as a covariate, and patient as a random effect
- Response variable: change from baseline

Note: If any lab measurements above are (1) below the quantification limit (eg <QL), $\frac{1}{2} \times$ QL will be used instead for calculation; (2) above the quantification limit (eg >QL), $1.1 \times$ QL will be used instead for calculation, if deemed appropriate after review of data. All these lab fasting measurements will be reported in both SI Units and conventional units.

Insulin Sensitivity

Secondary PD measures to assess the effect of tirzepatide 15 mg versus placebo on insulin sensitivity:

- change from baseline to Week 18 in insulin sensitivity indices assessed during sMMTT:
 - o **HOMA2-IR** (insulin resistance as measured by the HOMA2 method using fasting glucose [mmol/L] and fasting insulin [pmol/L] for calculation) (Hill et al. 2013)
 - Fasting measurement of glucose and insulin will be the mean of non-missing measurements at -10 and -1 minutes of sMMTT
 - Serum glucose and serum insulin are collected during sMMTT and used for calculation of HOMA2-IR and indices below.
 - If glucose or insulin values are outside of ranges of inputs in HOMA2-IR lookup table, HOMA2-IR will be missing.

Matsuda Index (postprandial insulin sensitivity from sMMTT) (Schlichtkrull et al. 1965; Matsuda and DeFronzo 1999; Service and O'Brien 2001)

$$ISI-Matsuda = \frac{10,000}{\sqrt{G_0*I_0*\frac{total\ glucose\ AUC_{0-4hr}}{4hr}*\frac{total\ insulin\ AUC_{0-4hr}}{4hr}}}$$

where G_0 and I_0 are the glucose concentration (mg/dL) and insulin concentration (μ U/mL) at 0 minute (fasting).

Note: Fasting measurement will be the mean of non-missing measurements at -10 and -1 minutes of sMMTT.

o OGIS Index (Oral Glucose Insulin Sensitivity Index) (Mari et al. 2001)

$$OGIS = \frac{1}{2} \times \left(B + \sqrt{B^2 + 4p_5p_6(G_{120min} - G_{CLAMP})Cl_{OGTT}} \right)$$

Where

$$B = [p_5(G_{120min} - G_{CLAMP}) + 1] \times Cl_{OGTT}$$

$$Cl_{OGTT} = p4 \frac{p_1D_0 - V(G_{180min} - G_{120min})/60min}{G_{120min}} + \frac{p_3}{G_0}$$

$$I_{120min} - I_0 + p_2$$

Where
$$p_1 = 289, p_2 = 270, p_3 = 14,000, p_4 = 440, p_5 = 0.000637, p_6 = 117$$

 D_0 is an oral glucose dose (expressed in grams per square meter)

(D₀ = carbohydrate intake [gram] during sMMTT / BSA [m²], where Gehan and George body surface area formula is BSA=0.1640443958298 × weight[kg]^{0.515} × (height[cm]/100)^{0.422} [Bailey and Briars 1996])

V=10,000 mL/m² (the total glucose distribution volume)

$$G_{CLAMP} = 90 \text{ mg/dL}$$

 $G_0 = \text{glucose concentration (mg/dL) at 0 minute (fasting)}.$

 I_0 = insulin concentration ($\mu U/mL$) at 0 minute (fasting).

 G_{120min} = glucose concentration (mg/dL) at 120 min

 I_{120min} = insulin concentration ($\mu U/mL$) at 120 min

 G_{180min} = glucose concentration (mg/dL) at 180 min

Note: Fasting measurement will be the mean of non-missing measurements at -10 and -1 minutes of sMMTT.

Stumvoll Index (Stumvoll et al. 2000; Stumvoll et al. 2001)
 Stumvoll ISI = 0.222 - 0.00333 BMI - 0.0000779 I_{120min} - 0.000422 Age

Where I_{120min} = insulin concentration (pmol/L) at 120 min

The above insulin sensitivity parameters during sMMTT will be analyzed using ANCOVA to compare the effect of tirzepatide versus placebo:

- ➤ Independent variables: treatment as a factor, baseline as a covariate
- Response variable: change from baseline to Week 18.

Glucose Control

Secondary PD measures to assess the effect of tirzepatide 15 mg versus placebo on parameters of glucose control:

- change from baseline to Week 18 in fasting and postmeal serum glucose during sMMTT
 - fasting glucose
 - mean of nonmissing glucose measurements at -10 and -1 minutes of sMMTT
 - o total glucose AUC_{0-4hr}
 - o incremental glucose AUC_{0-4hr}

Note: See Section 6.9.1 for AUC calculation details. All these glucose parameters will be reported in the SI Units and conventional units.

The above glucose parameters during sMMTT will be analyzed using ANCOVA to compare the effect of tirzepatide versus placebo:

- Independent variables: treatment as a factor, baseline as a covariate
- Response variable: change from baseline to Week 18.

Time profile plots of serum glucose levels (mean \pm SD) during sMMTT (over 11 time points) will be provided by treatment for baseline and Week 18.

• change from baseline through Week 18 in HbA1c

For HbA1c, it is scheduled to be measured at baseline (Day -4) and twice postbaseline (Day 57 [Week 9] and Day 122 [Week 18]). It will be analyzed in a similar manner to secondary PD analysis on body weight using MMRM:

- ➤ Independent variables: treatment, time, and treatment-by-time interaction as fixed effects, baseline HbA1c as a covariate, and patient as a random effect
- Response variable: change from baseline in HbA1c

Note: HbA1c will be reported in % and mmol/mol, where

$$HbA1c (mmol/mol) = 10.93 \times HbA1c (\%) - 23.5$$

Inferential statistics includes LS means and standard error of the measure for each treatment (tirzepatide, placebo), and the estimated treatment difference (tirzepatide - placebo), corresponding 2-sided 95% CI, and associated p-value.

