**Table GPGU.1. Objectives and Endpoints**

Objectives	Endpoints
Primary To assess the effect of tirzepatide versus placebo on SMR after 18 weeks ( $\pm 1$ week) of treatment	
 
The change from baseline to Week 18 in SMR, as measured in the respiratory chamber (whole-room calorimetry)
 

Secondary To assess the effect of tirzepatide versus placebo after 18 weeks ( $\pm 1$ week) of treatment: 
 
Appetite and food intake
 
Energy expenditure
 
Substrate oxidation rates
 
Body weight and body composition
 
Lipid metabolism
 
	
 
The change from baseline to Week 18 in appetite VAS
 
The change from baseline to Week 18 in food intake as assessed by ad libitum meal test
 
The change from baseline to Week 18 in 24-hour EE
 
The change from baseline to Week 18 in 24-hour RQ
 
The change from baseline to Week 18 in sleep RQ
 
The change from baseline to Week 18 in duration of periods with <math>RQ < 0.80</math>
 
The change from baseline to Week 18 in fat, protein, and carbohydrate oxidation
 
The change from baseline to Week 18 in BW
 
The change from baseline to Week 18 in body fat-free mass
 
The change from baseline to Week 18 in body fat mass
 
The change from baseline to Week 18 in the percentage of body fat mass
 
The change from baseline to Week 18 in triglycerides, cholesterol, LDL, VLDL, and HDL cholesterol, FFA, glycerol, 3-hydroxybutyrate, and acylcarnitines assessed during sMMTT
 
The change from baseline to Week 18 in ApoB-48, ApoB-100, ApoC-III, and LPL during sMMTT
 
The change from baseline to Week 18 in fasting concentration of leptin, adiponectin, IGFBP 1 and 2
 

Objectives	Endpoints
Secondary (continued) 
 
Insulin sensitivity
 
	
 
The change from baseline to Week 18 in fasting insulin resistance (as measured by the HOMA2 method [HOMA2-IR]) and postprandial insulin sensitivity indices (Matsuda, OGIS, and Stumvoll) assessed during sMMTT
 

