#### **10.3.3.2. Pharmacodynamic Statistical Inference**

The primary endpoint (SMR) will be analyzed using an analysis of covariance model (ANCOVA) to compare the effect of tirzepatide versus placebo. The dependent variable to be used in the model will be the change from baseline to 18 weeks in SMR. The independent variables will include treatment as a factor, baseline SMR and body composition parameter(s) as covariates. The primary analysis will be performed in all randomized subjects with evaluable data (modified intent-to-treat [mITT] population). Similar analysis will also be performed in subjects who reach the BW target range of  $-10\% (\pm 2\%)$  at Week 18 as a sensitivity analysis.

Other PD parameters that are scheduled to be measured only once postbaseline will be analyzed using a similar ANCOVA model with baseline measurement and treatment group as covariates. For parameters that are measured in the respiratory chamber, an adjustment for body composition parameter(s) as covariates may be applied if deemed appropriate. If the response is positive for all subjects and highly skewed, a log-transformation may be considered. Other parameters that are positive and skewed may be log-transformed.

The PD parameters that are scheduled to be measured at least twice postbaseline will be analyzed using a mixed-model repeated-measure method with restricted maximum likelihood estimation. The model will include the treatment, visit, and treatment-by-visit interaction as fixed effects, baseline value of the dependent variable as a covariate, and subject as a random effect. An unstructured variance-covariance matrix will be used to model the within-subject effects.

All PD analyses will be performed in the mITT population and selected analyses also on-BW-target population. All analyses will show least squares means of each treatment and the treatment difference in the original scale as well as standard error and 95% confidence interval. All tests will be done at the 2-sided 0.05  $\alpha$  level unless otherwise specified.

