6.2. General Considerations

Statistical analysis of this study will be the responsibility of Eli Lilly and Company (Lilly) or its designee. Any change to the statistical methods described in the protocol will require a protocol amendment only if it changes a principal feature of the protocol. Any other change to the statistical analyses and the justification for the change will be documented in SAP.

Unless otherwise specified, safety analyses will be conducted on the safety population (Table GPGU.6.1), and pharmacodynamic (PD) analyses will be conducted on the PD analysis set (Table GPGU.6.1).

Unless otherwise specified, baseline is defined as the last scheduled non-missing measurement collected during Visit 1 (screening) and Visit 2 (lead-in) before first dose.

Unless otherwise noted, all tests of treatment effects will be conducted at a 2-sided alpha level of 0.05, and the confidence interval (CI) will be calculated at 95%, 2-sided.

Unless otherwise specified, Week 18 represents Week 18-visit (Visit 20).

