6.9.2. Pharmacodynamic Statistical Inference

Unless specified otherwise, PD parameters at baseline and post baselines, as well as change from baseline values, will be summarized by treatment, and the change from baseline to Week 18 will be analyzed.

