6.13. COVID-19 Impact Assessment

A listing of subjects with adverse events related to COVID-19, including death due to COVID-19, serious COVID-19 adverse events, and COVID-19 adverse events, may be provided. Protocol deviations that study disruptions related to COVID-19 may be described in CSR.

7. Unblinding Plan

The blinding/unblinding plan is not part of this SAP. The approved blinding/unblinding plan is stored in Leo.

8. Changes from the Protocol Specified Statistical Analyses

Changes from the protocol specified statistical analyses are as follows:

- In protocol Section 1 and Section 10.3.3.2, it states "The primary analysis will be performed in all randomized subjects with evaluable data (modified intent-to-treat [mITT] population)". It is clarified in this SAP that PD analyses will be conducted on the PD analysis set (ie evaluable data from all randomized subjects who are exposed at least 1 dose of study drug). This is consistent with protocol Section 10.3 "Pharmacodynamic analyses will be conducted on data from all subjects who receive at least 1 dose of the IP and have evaluable data."
- In protocol Section 10.1 Sample Size Determination, it is updated to "Up to 56 subjects are planned to be randomized so that approximately 46 subjects complete the study assuming 15% discontinuation rate. These 56 subjects will be randomized to QW tirzepatide or placebo in a 1:1 ratio. The estimated standard deviation of the change in SMR from baseline is 117 kcal/day (Heilbronn et al. 2006). With an expected treatment difference of 100 kcal/day, this provides at least 80% power for the comparison of tirzepatide versus placebo based on 2 sample t-test using 2-sided test at alpha level of 0.05 for the assessment of the primary endpoint."
- In protocol appendix Section 6.4, it states "The Food Preference Questionnaires (FPQ) (Geiselman et al. 1998) assesses preferences for 72 foods in a 2 (high-fat, low-fat) by 3 (high-simple sugar, high-complex carbohydrate, low-carbohydrate/high-protein) matrix". It is updated and clarified in this SAP "The macronutrient self-selection paradigm (MSSP) is an instrument that has to be updated very frequently because of food availability in the grocery stores. During the updates, in the current version of FPQ used in CRF for this study contains 73 food items (where 13 food items in low fat/high sugar category)."

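### SAP 6.9.2.2 tests substrate oxidation only relative to 24-hour energy expenditure, so the g/day endpoint it names has no test, and SAP Section 8 does not record or justify the substitution

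*SAP*

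**What the plan says.** - Protocol Table GPGU.1 gives the endpoint as "The change from baseline to Week 18 in fat, protein, and carbohydrate oxidation". The formulas in Protocol 9.1.2 contain no division by EE.
- SAP 6.9.2.2 lists each substrate in absolute units, for example "change from baseline to Week 18 in fat oxidation (g/day"). It then says these parameters will be analysed in two steps. Step 1 computes "Adjusted oxidation rate (g/day) = oxidation rate (g/day) / 24-hr EE (kcal/day) * 1000 (kcal/day"). Step 2 is an ANCOVA on the change in that adjusted rate, with treatment and the baseline adjusted rate. No model is given for unadjusted g/day.
- Just before this, the respiratory quotient (RQ) endpoints are tested as measured: "Response variable: change from baseline to Week 18 in RQ parameter".
- For parameters measured in the respiratory chamber, Protocol 10.3.3.2 says that "an adjustment for body composition parameter(s) as covariates may be applied if deemed appropriate". It mentions no ratio to EE.
- SAP 6.9.2 has a general rule that pharmacodynamic parameters, "as well as change from baseline values, will be summarized by treatment, and the change from baseline to Week 18 will be analyzed".
- SAP 6.2 states: "Any other change to the statistical analyses and the justification for the change will be documented in SAP". Section 8 opens with "Changes from the protocol specified statistical analyses are as follows" and gives four items: the analysis set, the sample size text, the food preference questionnaire and treatment compliance. The oxidation ratio is not among them.

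**The concern.** Dividing by 24-hour EE changes the question from how many grams are oxidised to what share of expenditure each fuel supplies. The denominator is measured after randomisation, is a secondary endpoint with its own models in SAP 6.9.2.2, and is hypothesised in Protocol 3.2 to respond to tirzepatide. A reader who sees a significant result under the endpoint's name could take it to mean more or fewer grams oxidised, which the analysis does not test. The reverse also holds: a null adjusted result could be read as no change in oxidation when grams had changed in step with EE. Nothing in the plan warns of either, because the substitution is not recorded as a change and no reason is given for it.

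**Working it through.** **The plan's own figure.** No power or effect size is stated for oxidation. The only stated power, at least 80% for sleep metabolic rate (SMR), reproduces: 23 per arm, difference 100 and SD 117 kcal/day give 80.9% by noncentral t (82.6% by normal approximation). It says nothing about this endpoint. I borrow only the 100 kcal/day as a plausible scale for an EE difference.

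**Step 1: how EE and oxidation are tied.** The formulas are in SAP 6.9.1, with F, C and P for fat, carbohydrate and protein oxidation and N for urinary nitrogen:
- EE = 3.941 VO2 + 1.106 VCO2 − 2.17 N, with P = 6.25 N
- F + 0.324 P = 1.689 (VO2 − VCO2)
- C + 0.375 P = 4.113 VCO2 − 2.907 VO2

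Solving the last two for the gases, using 4.113 − 2.907 = 1.206:
- VO2 = [(C + 0.375 P) + (4.113/1.689)(F + 0.324 P)] / 1.206
- VCO2 = VO2 − (F + 0.324 P)/1.689

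Substituting into the EE formula gives **EE = 9.536 F + 4.185 C + 4.312 P**. The protein coefficient is 0.324 × 9.536 + 0.375 × 4.185 − 2.17/6.25 = 4.312. Two consequences follow. EE cannot differ while all three oxidation rates are equal. The three adjusted rates always satisfy 9.536 F′ + 4.185 C′ + 4.312 P′ = 1000, so only two are free.

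**Step 2: two ways to reach an EE lower by 100 kcal/day in one arm.** Arms are taken as equal at baseline, so the Week 18 difference equals the difference in change. The documents give no EE level, RQ or protein share. I assume EE 1800 to 2600 kcal/day, RQ 0.82 to 0.88 and protein at 15% of EE. The table shows EE 2200 and RQ 0.85.

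| | Fat | Carbohydrate | Protein |
|---|---|---|---|
| Reference arm, g/day | 90.8 | 240.0 | 76.5 |
| Reference arm, per 1000 kcal/day | 41.3 | 109.1 | 34.8 |
| A: same fuel mix, difference in g/day | −4.1 | −10.9 | −3.5 |
| A: difference in adjusted rate | 0 | 0 | 0 |
| B: fall through carbohydrate only, difference in g/day | 0 | −23.9 | 0 |
| B: difference in adjusted rate | +4.8% | −5.7% | +4.8% |

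In A every rate is multiplied by 2100/2200, so the ratio is unchanged. Over the whole assumed range the hidden differences are 3.0 to 5.2 g/day for fat, 8.4 to 13.4 for carbohydrate and 3.5 for protein.

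In B carbohydrate falls by 100/4.185 = 23.9 g/day. Fat and protein grams are unchanged, so their ratios rise by 100/(EE − 100): 100/1700 = 5.9% at EE 1800, 100/2100 = 4.8% at 2200, and 100/2500 = 4.0% at 2600. If EE were instead higher by 100 through carbohydrate only, these ratios would fall by 100/(EE + 100), which is 5.3% to 3.7%.

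**Step 3: the scales can disagree in sign.** If fat falls from 90.8 to 89.8 g/day while EE falls from 2200 to 2100, the adjusted rate goes from 41.3 to 89.8/2100 × 1000 = 42.8. Grams are down and the ratio is up.

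**Step 4: rejection rates.** I simulated the ANCOVA with 23 per arm, 1,500 runs per scenario and a 100 kcal/day EE difference. Assumptions: baseline EE mean 2200, SD 300; fat and protein energy shares 40% and 15%, SDs 6 and 1.5 points; change in EE mean −150, SD 117; within-subject changes in share with SDs 4 and 1.2 points.

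| Scenario | Fat g/day | Fat adjusted | Protein g/day | Protein adjusted |
|---|---|---|---|---|
| A: same mix | 28% | 5% | 37% | 5% |
| B: carbohydrate only | 5% | 39% | 4% | 55% |

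The percentages depend on the assumed SDs. The pattern follows from Step 2.

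**The case against.** The best defence is that the energy-relative rate is a sound measure of fuel use, and in one respect the cleaner one. Protocol Appendix 6, Section 6.6 matches chamber feeding to expenditure, so grams oxidised tend to scale with EE. With identical fuel mix, g/day picks up the EE difference (28% and 37% rejection in Step 4) and the ratio does not. Absolute EE already has its own analysis, and the objective is substrate oxidation rates, reported alongside RQ. This stands as a reason to keep the adjusted analysis. It does not explain why the variable named as the endpoint has no test. For food intake the same SAP section tests grams, kcal and percent of energy together.

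The defence can also say that the protocol leaves calculation details to the SAP, that SAP 6.9.2.2 states the ratio openly, and that the general rule in 6.9.2 should leave g/day visible descriptively. That is fair, and it narrows the documentation gap to a missing justification and a missing Section 8 entry.

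A reader might infer three stronger things that the documents do not support:
- That an EE difference alone creates a false oxidation effect. The SAP's formulas rule this out: at constant mix the ratio change is exactly zero. An illustration that fixes fat grams while EE falls has changed the fuel mix, and the difference in fat's share is then real.
- That the g/day unit of the adjusted rate is wrong. The 1000 carries kcal/day, which cancels. The label is consistent, though easy to confuse with the raw endpoint.
- That the ratio only repeats RQ. The adjusted rates have two free dimensions, RQ is one number, and protein comes separately from urinary nitrogen.

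**Conclusion.** The point holds as a mismatch between the named endpoint and the analysed variable, undocumented as a change. The only inferential analysis of oxidation is on a share-of-expenditure scale that the protocol does not provide for, and the g/day endpoint has no test. That scale shows nothing when grams change in proportion to EE. It shifts a substrate with unchanged grams by about 4% to 6% when EE is 100 kcal/day lower through another substrate.

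The identity linking EE and oxidation comes from the SAP's formulas and needs no assumption. The 4% to 6% rests on the assumed EE range and on an EE difference borrowed from SMR planning. Neither scale is wrong; they answer different questions. The matter affects one family of secondary endpoints and leaves the primary SMR analysis untouched.

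**What to change.** 1. In SAP 6.9.2.2, add an ANCOVA on change from baseline to Week 18 in unadjusted g/day for each of fat, protein and carbohydrate, with treatment and baseline g/day, and name these as the analysis of the endpoint as listed.
2. Keep the adjusted analysis beside them, described as oxidation standardised to 1000 kcal/day of EE (fuel share). State that the two sets will be interpreted together with the 24-hour EE result.
3. Add an entry to SAP Section 8 that lists the adjusted analysis and gives the reason for it.

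The cost is three extra ANCOVAs on data the site already supplies and a short Section 8 entry. No new data collection is needed.
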